#### Level 4: Number of days with solicited adverse events

The number of days with the adverse event is defined irrespective of severity. This means at least ‘mild’ solicited adverse event that are assessed qualitatively and  $\geq 25$  mm for erythema, induration, and ecchymosis. If a solicited adverse event continues beyond Day 7, the period after Day 7 is added as an unsolicited adverse event.

The frequency distribution of the number of days will be provided in a summary table by vaccine and by adverse event.

#### Level 5: Solicited adverse events, occurrence of at least one event by category (local, systemic) and interval.

The **occurrence of at least one solicited adverse event** is defined as “any” for a subject if he/she reports greater than “none” for qualitatively assessed solicited systemic AEs and/or  $\geq 25$  mm for erythema, ecchymosis and induration for the respective event and “none” otherwise. The occurrence of at least one solicited adverse event (i.e., none versus any) will be summarized by category (i.e., local, systemic, any), by vaccine group, by vaccination (after each vaccination and after any vaccination) and by time interval.

Medications to treat or prevent pain or fever will be summarized by frequencies and percentages of subjects reporting use of the medications by interval 30 min, Day 1 – 3 (excluding 30 minutes after vaccination), Day 4 – 7, Day 1 – 7 (excluding 30 minutes after vaccination).

For details please refer to [section 7.1.1 of the Protocol](#).

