6.5 Solicited Safety Measurements

The term “reactogenicity” refers to selected signs and symptoms (“AEs”) occurring in the hours and days following a vaccination, to be collected by the subject for 7 consecutive days, using a pre-defined check list in a diary card (i.e. solicited AEs), see [section 3.2.5.3](#) and [section 8.1](#).

The following AEs are included in the diary check list. Each AE is to be assessed using the scoring system shown in [Appendix B](#) and [Appendix C](#).

Solicited local adverse events:

Injection site induration, erythema, ecchymosis and pain.

Solicited systemic adverse events:

Nausea, generalized myalgia, generalized arthralgia, headache, fatigue, chills, loss of appetite, malaise and fever (derived from measured body temperatures (defined as body temperature ≥ 38.0 °C [≥ 100.4 °F])).

Other solicited adverse events:

Body temperature (summarized by route of measurement and in 0.5 °C increments from 36.0 °C) and the use of analgesics/ antipyretic medication for prophylaxis or treatment.

The study staff must review the diary card with the subject at the following visit (see [section 3.2.5](#)) and must directly record the solicited local and systemic AEs, and other solicited AEs on the appropriate Local and Systemic AEs eCRF. As described in [section 3.4.1](#), all solicited AEs that are legible must be recorded verbatim in the eCRFs, even if the values do not appear to be plausible.

If a solicited local or systemic AE continues beyond day 7 after vaccination, it will also be recorded as an AE on the AEs eCRF.

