### **13.2 Solicited Local and Systemic Adverse Events**

Only solicited local and systemic adverse events reported in the diary card will be analyzed. Implausible measurements will not be taken into consideration in the analysis but listed in the Appendix of the CSR (see [section 6.3](#) of this document).

Solicited adverse events will be collected at 30 minutes, Day 1 (after 30 minutes) and then daily until Day 7 using structured diaries. The analyses of solicited adverse events will be done separately for 30 minutes and based on the intervals: Day 1-3 (with and without the 30-minute interval), Day 4-7, and Day 1-7 (with and without the 30-minute interval). In addition solicited adverse events ongoing after Day 7 will be presented as unsolicited AE.

For erythema, induration, and ecchymosis recorded originally as diameters (mm), the following categorization will be used to summarize the data:

Grade 0 (<25 mm), any (25-50 mm [Grade I], 51-100 mm [Grade II], >100 mm [Grade III]).

Injection site pain and systemic AEs (except fever) occurring for the 7 days including each vaccination will be summarized according to “mild”, “moderate” or “severe”.

Each solicited local and systemic AE will also be further summarized as “none” versus “any”.

Body temperature will be broken down by route of measurement according to the recommendations of the Brighton collaboration and will be summarized according to the 2 schemes described below:

- by 0.5 °C increments: <36.0, ≥36.0-<36.5, ≥36.5-<37.0, ≥37.0-<37.5, ≥37.5-<38.0, ≥38.0-<38.5, ≥38.5-<39.0, ≥39.0-<39.5, ≥39.5-<40.0, ≥40.0°C
- <38.0, ≥38.0 °C

Fever, defined as a body temperature of ≥38°C irrespective of route of measurement, will be integrated to the summaries as an indicator of a systemic adverse event.

The analyses will encompass summaries of the data on five levels:

1. Daily reports of subjects with solicited adverse events.
2. Time of first onset of solicited adverse events (excluding 30 min measurement).

3. Solicited adverse events, maximum event severity by event and interval Day 1-3, Day 4-7, and Day 1-7, each without 30 min.
4. Duration of solicited adverse events.
5. Solicited adverse events and indicators of solicited adverse events, occurrence of at least one event by category (local, systemic) and interval Day 1-3, Day 4-7 and Day 1-7, each without 30 min.

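### SAP 13.2 Level 5, as written, leaves injection-site pain out of the definition of any solicited AE, so a subject whose only reaction is pain counts as *none* in the *local* and overall *any* composites

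*SAP*

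**What the plan says.** SAP 13.2 sets out five levels of solicited-AE summary. Level 5 defines the composite of at least one event. A subject counts as *any* with a grade above none "for qualitatively assessed solicited systemic AEs and/or" a reading of at least 25 mm for erythema, ecchymosis or induration, and counts as *none* otherwise. The result "will be summarized by category (i.e., local, systemic, any), by vaccine group, by vaccination", the last meaning after each and after any vaccination, and by time interval.

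Other places bear on this rule:

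- Protocol 6.5 lists the solicited local AEs: "Injection site induration, erythema, ecchymosis and pain".
- Protocol Appendix B grades pain by its effect on activity and the other three by size in cm.
- SAP 13.2, Level 4, counts days with at least a mild "solicited adverse event that are assessed qualitatively", without limiting this to systemic events.
- The general text of SAP 13.2 treats pain like the systemic events: "Injection site pain and systemic AEs (except fever) occurring for the 7 days including each vaccination will be summarized according to" three severity grades. It also calls for a none-versus-any summary of each individual local and systemic event.
- The same text says that fever, a measured variable, "will be integrated to the summaries as an indicator of a systemic adverse event".
- Protocol 7.4.3.2 promises summary tables for the occurrence of any local or systemic AE.

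**The concern.** The Level 5 rule feeds a *local* category and an overall *any* category, yet its wording omits the only local reaction that is graded qualitatively. The *local* composite would then measure only skin reactions of 25 mm or more.

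Safety and tolerability is a primary objective, and protocol 7.1.4 makes the percentage of subjects with solicited local AEs a safety endpoint. Programmed literally, the composite would not be that percentage. It could also fall below the pain percentage shown elsewhere in the same report. If pain without a skin reaction differs in frequency between vaccine and placebo, the descriptive contrast between groups is distorted as well.

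**Working it through.** The plan states no figure for this point, so there is nothing to reproduce. The check applies the Level 5 rule literally.

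**Step 1. Which local events can trigger *any*?**

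| Solicited local AE (protocol 6.5) | How assessed (Appendix B) | Systemic-grade route | 25 mm route |
|---|---|---|---|
| Induration | size | no | yes |
| Erythema | size | no | yes |
| Ecchymosis | size | no | yes |
| Pain | interference with activity | no | no |

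Pain is the only one of the four that enters by neither route.

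**Step 2. Hypothetical subjects.** Each entry reads local / systemic / overall.

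| Subject | Level 5 sentence alone | With pain and fever included |
|---|---|---|
| Severe pain only | none / none / none | any / none / any |
| Mild pain and headache | none / any / any | any / any / any |
| Pain and 30 mm erythema | any / none / any | any / none / any |
| Fever only | none / none / none | none / any / any |
| No reaction | none / none / none | none / none / none |

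Fever also falls outside the Level 5 sentence, but the general text of 13.2 brings it in expressly. Taking that text into account, the *systemic* composite loses nothing. No comparable sentence brings pain into the composite.

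**Step 3. Percentages affected.** Two categories (*local*, *any*) × three vaccination rows (first, second, any) × the three intervals listed for Level 5 (Day 1-3, 4-7, 1-7) = 2 × 3 × 3 = 18 per vaccine group. If the six intervals in the general text of 13.2 apply (30 minutes; Day 1-3 with and without it; Day 4-7; Day 1-7 with and without it), the count is 2 × 3 × 6 = 36. Neither count includes the subgroup repeats in SAP 8.6.

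**Step 4. Size in each cell.** Let p_pain be the proportion with any pain and p_skin the proportion with at least one skin reaction of 25 mm or more, on a common denominator.

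- Shortfall in *local* = P(pain or skin) − P(skin) = P(pain and no skin reaction).
- Bounds: max(0, p_pain − p_skin) ≤ shortfall ≤ min(p_pain, 1 − p_skin).
- Shortfall in overall *any* = P(pain and no other solicited reaction), which cannot exceed the *local* shortfall.
- Shortfall in *systemic* = 0.

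Under the literal rule the *local* composite equals p_skin. Whenever p_pain exceeds p_skin, the report would show fewer subjects with any local reaction than with pain.

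**Step 5. Scale, by assumption only.** The documents give no rates. If pain were the only local reaction in 10% to 50% of the 2394 planned vaccine recipients, the *local* composite would miss 0.10 × 2394 ≈ 239 to 0.50 × 2394 = 1197 subjects. This range only illustrates scale and is not an estimate.

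**Step 6. Smaller mismatches in the same section.**

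- Protocol Appendix B, footnote 8, says a 1 to 2.4 cm range will be summarized. SAP 13.2 has no such row and places those readings in Grade 0 (below 25 mm).
- SAP 13.2 says the analyses "will be done separately for 30 minutes and based on the intervals: Day 1-3 (with and without the 30-minute interval"), but its list of levels then gives Level 5 as "occurrence of at least one event by category (local, systemic) and interval Day 1-3, Day 4-7 and Day 1-7, each without 30 min". Level 3 carries the same restriction. Protocol 7.1.4 and 7.4.3.2 and SAP 8.2.1 all include the 30-minute variants.
- Level 5 ends by referring to protocol 7.1.1, which holds the primary immunogenicity endpoints.

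**The case against.** The strongest reply is that the rest of the plan makes the intention clear. Protocol 7.4.3.2 requires an any-local-or-systemic summary, protocol 6.5 lists pain as local, and SAP 13.2 gives every local event a none-versus-any classification. A sensible programmer would include pain, and the table shells, which are a separate document, may already do so. The pain-specific tables are intact, and an any-local percentage below the pain percentage would expose the error. All safety analysis is descriptive.

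Much of this is fair. It supports reading the text as a slip, and it means the effect on reported tables is not certain. It does not cure the definition. The none-versus-any sentence in 13.2 works event by event, and only Level 5 defines the composite. Its reference to the respective event does not add pain to the list. To include pain, a programmer would have to depart from an explicit rule that assigns everything else to *none*. The solicited-AE tables are also not among the key programs named for second-programmer review in SAP 16.

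Three narrower objections stand:

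- The count of 18 depends on the three-interval list and says nothing about the size of the understatement.
- The 1 to 2.4 cm range is also missing from protocol 7.4.3.2, so that conflict lies partly within the protocol.
- The intended target of the wrong cross-reference is not certain. It could be 7.1.4 (safety endpoints) or 7.4.3.2 (analysis of solicited events, including analgesic and antipyretic use).

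**Conclusion.** The concern holds. As written, Level 5 returns *none* for a subject whose only solicited reaction is pain, in both the *local* and the overall *any* composites. A subject with pain plus a graded systemic event is lost from *local* but kept in overall *any*. One of four local AEs and two of three categories are affected: 18 percentages per vaccine group under the intervals listed for Level 5.

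The understatement cannot be quantified from the documents; it follows the expressions and bounds above, given a common denominator and literal programming. The per-event pain tables and the *systemic* composite are unaffected. No hypothesis, significance level, power or success criterion changes. It should be fixed because the stated rule gives a wrong percentage for a primary safety objective.

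**What to change.** Reword the Level 5 definition in SAP 13.2 so that a subject counts as *any* with one or more of the following, and as *none* otherwise:

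- injection-site pain, or a qualitatively graded systemic event, above none;
- fever of 38.0 °C or higher;
- erythema, ecchymosis or induration of 25 mm or more.

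Pain and the skin reactions feed *local*, the graded systemic events and fever feed *systemic*, and all of them feed overall *any*. Keep 25 mm, which is the protocol's own lowest grade in 7.4.3.2 and Appendix B.

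In the same revision:

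- add a descriptive 10 to 24 mm row for the three measured reactions, as footnote 8 says, and align protocol 7.4.3.2 with it;
- reconcile the 30-minute wording for Levels 3 and 5 with the general text of 13.2, SAP 8.2.1, and protocol 7.1.4 and 7.4.3.2;
- replace the reference to protocol 7.1.1, with 7.1.4 the likely target, after checking whether 7.4.3.2 was meant.

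The cost is SAP wording, one extra row per measured reaction, and table shells for the 30-minute variants. No new data are needed. Make the change before unblinding so that the composite is prespecified.

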### **13.3 Unsolicited Adverse Events**

The first-line analysis will use unsolicited adverse event data from all reporting sources combined. A second-line analysis will encompass the analysis of unsolicited adverse events by source.

All the unsolicited adverse events occurring during the study, judged either as probably related, possibly related, or not related to vaccination by the investigator, will be recorded. The original verbatim terms used by investigators to identify adverse events in the case report forms (CRFs) will be mapped to preferred terms using the MedDRA dictionary. The unsolicited adverse events will then be grouped by MedDRA preferred terms into frequency tables according to system organ class. Adverse events judged by the investigator as at least possibly related to study vaccine will be summarized by vaccine group, according to system organ class and preferred term within system organ class. When an unsolicited adverse event occurs more than once for a subject, the maximal severity and strongest relationship to the vaccine group will be counted.

Only vaccine-emergent adverse events (see [section 8.7](#) for definition) will be analyzed, i.e., excluding those after a subject has given informed consent but before vaccination. The selection of unsolicited adverse events and the assignment to time intervals will be done by day of onset and not by days ongoing/persisting.

The summaries will be presented by period of onset and will include frequency distributions of the different adverse events:

- Onset between Day 1 and Day 22.
- Onset between Day 23 and Day 43.
- Onset between Day 1 and Day 43.
- Onset between Day 44 and study termination.
- Onset between Day 1 and study termination.

The analysis of unsolicited adverse events comprises the following categories:

- Any unsolicited adverse event.
- Possibly or probably related unsolicited adverse events.
- Unsolicited adverse events leading to death.
- Serious adverse events.
- Possibly or probably related serious adverse event.
- Unsolicited adverse events leading to premature withdrawal from study.
- Unsolicited adverse events leading to dose change in study vaccination.
- Unsolicited adverse events leading to new onset of chronic disease (NOCD).
- Unsolicited adverse events of special interest (AESI), see [Appendix A of the protocol](#)
- Medically attended adverse events.

Solicited adverse events continuing beyond Day 7 will be coded by MedDRA and combined with the respective unsolicited adverse events.

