After each vaccination, all subjects will remain under medical supervision at the study site for at least 30 minutes to be monitored and evaluated for AEs. Subjects will be instructed on the measurement of local and systemic solicited AEs, including body temperature, and on the completion of the diary cards.

The diary cards will collect solicited and unsolicited AEs, and medication/vaccinations given from Day 1 to Day 7 (inclusive) and from Day 22 to Day 28 (inclusive). From Day 8 to 21 and from Day 29 to 42, only unsolicited AEs, solicited AEs that continue beyond Day 7 or 28, respectively, and medications/ vaccinations will be collected at the time of return to the clinic on Day 22 or 43, respectively.

In addition to these safety data, from Day 1 through Day 387 (inclusive) serious adverse events (SAEs), adverse events of special interest (AESIs), new onset of chronic disease (NOCD), AEs leading to vaccine/study withdrawal, medically attended AEs, associated concomitant medications for any of these events, and all vaccinations will be recorded. For full list of AESIs see [appendix A](#). These data will be captured through the diary card, by interview of the subject, and by review of available medical records.

Blood will be drawn from each subject for immunogenicity assessments before each vaccination (Day 1 and Day 22) and also drawn at clinic visits on Day 43 and Day 183. Blood drawn will be evaluated for antibody responses as measured by HI antibody responses and possibly also microneutralization (MN) antibody responses.

An interim analysis of immunogenicity will be performed for all subjects through the Day 43 visit. Site staff and Sponsor personnel involved in study conduct will remain blinded to treatment assignments for this interim analysis.

The final analysis will be performed when all data up to the study end (Day 387) are available. Analysis will be done on fully unblinded data by the Sponsor and all data will be presented in the final, cumulative study report. A Data Monitoring Committee (DMC) will not be used for this study.

To maintain the observer-blind design of the study for the two vaccine doses (Day 1 and Day 22), the roles and responsibilities of blinded and unblinded team members will be defined and maintained throughout the study. Safety assessments and study related procedures and monitoring thereof must be performed by blinded team members.

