3.2.5.6 Safety calls

Safety calls will be performed approximately 3, 4, 5, 7, 8, 9, 10.5, and 12 months after the first vaccination on Day 91, 122, 152, 217, 251, 285, 319, and 353 (see [Table 2, Time and Events Table](#)).

1. Safety calls should be done by a trained healthcare professional. These calls will follow a script which will facilitate the collection of relevant safety information. The subject will be interviewed according to the script, to obtain information relating to unsolicited AEs including SAEs, AESIs, NOCD, AEs leading to vaccine/study withdrawal, medically attended AEs, associated concomitant medications for any of these events, and all vaccinations. All safety information described by the subject must be written down in the source documents and not written on the script used for the telephone call (see [section 3.4.1](#)).
2. Record any relevant medical history as needed (see [section 6.2](#)).
3. Schedule the next study activity (clinic visit or safety call) with the subject.
4. Remind the subject to contact the site if there are any questions and to contact the site immediately (or as soon as the subject is medically stable) if the subject has a medical condition that leads to a hospitalization.

3.2.5.7 'For cause' visits

Not applicable for this study.

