6.6.3 Methods for Assessing and Recording AEs and SAEs

The period of observation for AEs extends from the time the subject signs informed consent until he or she completes the specified safety follow-up period, approximately 13 months after the first vaccination or terminates the study early (whichever comes first).

AEs occurring after the ICF is signed but prior to receiving study vaccine/product will be documented as an AE and recorded on the AEs eCRF and within source documents. However, AEs occurring prior to receipt of any study vaccine will be analyzed separately from “treatment emergent” AEs (AEs occurring after administration of the first study vaccine).

All AEs meeting criteria for reporting, regardless of severity, will be monitored by the investigator until resolution or stabilization. All subjects experiencing AEs - whether considered associated with the use of the study vaccine or not - must be monitored until symptoms subside and any abnormal laboratory values have returned to baseline, or until there is a satisfactory explanation for the changes observed, or until death, in which case a full pathologist’s report should be supplied, if possible. All findings must be reported on an AEs eCRF and on the VSAE form, if necessary, which is part of the Investigator Site File. All findings in subjects experiencing AEs must be reported also in the subject's medical records.

All SAEs which occur during the course of the study, whether considered to be associated with the study vaccination or not, must be reported **within 24 hours of the site becoming aware of the event** by telephone or fax to the Sponsor. Contact details for submitting SAEs to the Sponsor or its designee and instructions for completion of documentation will be provided in a handout located in the Investigator Site File.

All SAEs are also to be documented on the AE eCRF. Any medication or other therapeutic measures used to treat the AE will be recorded on the appropriate eCRF(s) in addition to the outcome of the AE.

After receipt of the initial report, representatives of the Sponsor will contact the investigator if it is necessary to obtain further information for assessment of the event.

All SAEs must be reported by the investigator to his/her corresponding EC or IRB and applicable regulatory authorities in accordance with institutional policy/regulatory requirements and adequate documentation of this notification must be provided to the Sponsor.

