7.1.4 Safety Endpoints

The measures for assessing safety and tolerability are as follows:

- Percentages of subjects with solicited local, solicited systemic and other AEs as measured for 7 days (inclusive) following each (1st and 2nd) and any (1st or 2nd) vaccination, by vaccine group (and calculated for several time intervals after vaccination⁷: 30 minutes, 1 to 3 days (without 30 min), 4 to 7 days, and 1 to 7 days (without 30 min), and 1 to 3 days (including 30 minutes) and 1 to 7 days (including 30 minutes).
- Percentages of subjects with any unsolicited AEs reported through 21 days after each (1st and 2nd) and any (1st or 2nd) vaccination by vaccine group.
- Percentages of subjects reporting SAEs, AESIs, NOCD, AEs leading to vaccine/study withdrawal, and medically attended AEs, and concomitant medications associated with these events as collected from Day 1 to Day 387, by vaccine group.

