#### **8.2.1 Safety Data**

For unsolicited adverse events, the entire study period will be divided into the following intervals: Day 1-22, Day 23-43, Day 1-43, Day 44-387, Day 1-387.

For solicited adverse events, the solicited study period 30 min - Day 7 after each vaccination will be divided into: 30 min, Day 1-3 (with and without the 30-minute interval), Day 4-7, and Day 1-7 (with and without the 30-minute interval).

No imputation of missing solicited or unsolicited AEs will be used. The percentage of subjects with missing solicited AE assessments and missing safety phone calls or safety assessment, including subjects who discontinued the study, will be reported for each time period.

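### Late and whole-study rates of any and related unsolicited AEs are tabulated without a label, although the protocol's main collection rules require full AE recording only to about the Day 43 visit

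*SAP*

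**What the plan says.** **Tabulation.** SAP 13.3 presents unsolicited AE summaries by five onset periods, two of which are "Onset between Day 44 and study termination" and "Onset between Day 1 and study termination". Its category list opens with "Any unsolicited adverse event" and then possibly or probably related events. No category is tied to a period. SAP 8.2.1 gives the same intervals, again without a category limit: "Day 1-22, Day 23-43, Day 1-43, Day 44-387, Day 1-387". Protocol 7.4.3.3 also asks for summaries of all reported AEs and of related AEs by observation interval.

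**Collection, main rules.** Protocol Table 2 marks the assessment of all AEs at Visits 1, 2 and 3 only. From Visit 4 to Visit 13 it marks only the row for selected categories. Section 3.1 agrees: "In addition to these safety data, from Day 1 through Day 387 (inclusive) serious adverse events (SAEs), adverse events of special interest (AESIs", and it goes on to new onset of chronic disease, AEs leading to withdrawal and medically attended AEs. The endpoint in section 7.1.4 is "Percentages of subjects with any unsolicited AEs reported through 21 days after each (1st and 2nd) and any (1st or 2nd) vaccination".

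**Collection, text pointing the other way.** Section 6.6.3 states: "The period of observation for AEs extends from the time the subject signs informed consent until he or she completes the specified safety follow-up period", which it puts at about 13 months. Section 3.2.5.6 says of the safety calls: "The subject will be interviewed according to the script, to obtain information relating to unsolicited AEs including SAEs". Sections 3.2.5.5, 3.2.5.8 and 3.9 have similar interview wording for the late visits and early termination. Protocol 7.4.3.3 and SAP 13.3 both say that AEs occurring during the study are all recorded.

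**The concern.** The SAP reports rates for periods in which, on the protocol's main collection rules, most ordinary AEs need not be recorded. A symptom on Day 120 that led to no medical visit and fell in no selected category would not have to be captured, but the Day 44 to termination table would show that subject as event-free. A low late rate could then be read as few events when it partly reflects narrower collection. It could not be compared with the Day 1-43 rate.

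The SAP's missing-data reporting would not reveal this. SAP 8.2.1 counts missed safety calls and assessments, so a subject who completed every call looks fully observed.

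The conflict within the protocol adds a second problem. A site working from section 6.6.3 may record the Day 120 symptom, and a site working from Table 2 may not. Evaluating safety and tolerability is a primary objective (protocol 2.1), so the absolute rates will be read closely even though the analysis is descriptive.

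**Working it through.** The plan states no figure for this point, so the check is a comparison of texts, some counts and one illustration.

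**1. Texts side by side**

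| Source | General unsolicited AEs | Selected categories |
|---|---|---|
| Protocol Table 2 | Visits 1, 2, 3 | Visits 1 to 13 |
| Protocol 3.1 | to the Day 43 visit | to Day 387 |
| Protocol 3.2.5.3 (diary) | 21 days, or to the evening before the next visit | not addressed |
| Protocol 5.4 (associated medication) | to Day 43 | to Day 387 |
| Protocol 7.1.4 (endpoint) | 21 days after each dose | to Day 387 |
| Protocol 6.6.3 and late interview text | can be read as to Day 387 | to Day 387 |
| SAP 8.2.1 and 13.3 (tables) | intervals to Day 387, no restriction | intervals to Day 387 |

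Five sources agree on a stop at about Day 43 for general AEs. The SAP tables run past it.

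**2. Contacts.** 5 clinic visits + 8 safety calls = 13 numbered visits; with 4 reminder calls the total is 17, as the protocol states. All AEs are assessed at 3 of the 13. The other 10 cover selected categories only.

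**3. Nominal days.** Day 44 to Day 387 is 387 − 44 + 1 = 344 days. 344/387 = 88.9% under selective collection and 43/387 = 11.1% under full collection.

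**4. Table cells.** SAP 13.3 lists 10 categories and 5 periods. If fully crossed, that is 10 × 5 = 50 cells. Two categories (any, related) in two periods give 2 × 2 = 4 affected cells, or 8%.

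**5. Visit windows.** Table 2 allows Visit 2 up to 30 days after the first dose (Day 1 + 30 = Day 31) and Visit 3 up to 30 days after the second (Day 31 + 30 = Day 61). Diary collection can therefore run past Day 44 in some subjects, so a calendar cut at Day 43 mixes the two collection regimes.

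**6. Possible size, by assumption only.** Let *p* be the proportion of subjects with any unsolicited AE by Day 43, with a constant hazard λ = −ln(1 − *p*)/43. Let *f* be the share of later AEs that fall in a collected category. None of these inputs is in the documents.

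- Day 44-387: full rate 1 − exp(−344λ); tabulated rate 1 − exp(−344*f*λ).
- Day 1-387: full rate 1 − exp(−387λ); tabulated rate 1 − exp(−43λ − 344*f*λ).

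With *p* = 20% and *f* = 30%, λ = 0.2231/43 = 0.00519 per day. For Day 44-387 the full rate is 83.2% and the tabulated rate 41.5%. For Day 1-387 they are 86.6% and 53.2%.

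Over *p* = 10-40% and *f* = 10-50%, the Day 44-387 full rate is 57-98% and the tabulated rate 8-87%. For Day 1-387 the ranges are 61-99% and 17-92%. If *f* = 1 the two rates coincide.

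**The case against.** The other side has four fair arguments.

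- **The stop at Day 43 is disputed.** A reader might infer that full AE collection certainly ends there. The documents do not settle it: section 6.6.3 and the interview text can be read as collection to Day 387, and on that reading the SAP intervals are right and Table 2 is out of line. This stands as a limit on certainty. It does not remove the problem, because while both texts remain, late recording may vary by site. Section 6.6.3 also speaks of AEs that meet criteria for reporting, which fits selective collection.
- **The crossing of categories and periods is partly inferred.** SAP 13.3 gives two separate lists, and the table shells are a separate document not available here. This stands against saying that the SAP spells out every cell. The crossing is still the natural reading of SAP 13.3 with protocol 7.4.3.3. The late period itself is not an error, since the selected categories need it.
- **The safety endpoint is intact.** A reader might infer that the primary safety results are compromised. They are not: the any-AE endpoint in section 7.1.4 stops 21 days after each dose and is served by the intervals up to Day 43. The endpoints that run to Day 387 are the selected categories.
- **The arms are treated alike.** A reader might infer a bias towards vaccine or placebo. The collection rules are the same in all arms, the study is observer-blind, randomization is stratified by center and the analysis is descriptive. No bias by design follows.

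The share of calendar days is also not a share of missed events. An AE counts as medically attended after any unscheduled visit to a healthcare professional, which narrows the gap.

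**Conclusion.** The point holds as one about interpretation and consistency. As written, the plan would show late and whole-study rates of any and related unsolicited AEs as complete when the best-supported collection rule makes them under-ascertained absolute rates. About 4 of 50 potential table cells are affected, covering periods in which 344 of the 387 nominal days have selective collection. The number of events missed cannot be derived from the documents; the illustrative ranges show only that it could be large or small.

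The conclusion assumes that Table 2 and the five matching texts govern, and that the SAP categories are crossed with its periods. If section 6.6.3 governs instead, the SAP rows could stand, but Table 2 and the sections that agree with it would need to change. The change should be made, but it does not threaten the protocol's endpoints.

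**What to change.** 1. **Protocol.** Reconcile section 6.6.3, the interview text in sections 3.2.5.5, 3.2.5.6, 3.2.5.8 and 3.9, and section 7.4.3.3 with Table 2, so that every site records the same AE categories after Visit 3.
2. **SAP 8.2.1 and 13.3.** Limit any and related unsolicited AE rates to the full-collection period. Anchor that period to 21 days after each vaccination or to the actual Visit 3, not to calendar Day 43.
3. **Late rows.** If they are kept to satisfy protocol 7.4.3.3, label them as covering collected categories only after Visit 3, and do not present the Day 1-387 any-AE figure as a complete rate.
4. **Unchanged.** Keep SAEs, related SAEs, AESIs, new onset of chronic disease, medically attended AEs, AEs leading to withdrawal and deaths through Day 387.

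The cost is SAP wording, table labels or fewer tables, and aligned wording in several protocol sections. The whole-study any-AE headline rate is lost or qualified.
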